### 16.1.10 Documentation of inter-laboratory standardization methods and quality assurance procedures

#### Certifications of Accreditation

Document	Expiration Date
Quality report by Vietnam Bureau of Accreditation (English Version)	14 October 2016
Quality report by Vietnam Bureau of Accreditation (Vietnamese Version)	14 October 2016
Pasteur Institute of Hochiminh City - Laboratory Respiratory Virus	24 January 2017
Pasteur Institute of Hochiminh City - Laboratory Respiratory Virus	17 October 2020
VidMederi Srl - Testing Laboratory	17 December 2017
VidMederi Srl - Medical Laboratory	21 May 2019
Criteria for Marked Vital Signs Abnormalities	NA

MINISTRY OF SCIENCE AND  
TECHNOLOGY  
**BUREAU OF ACCREDITATION**

**SOCIALIST REPUBLIC OF VIETNAM**  
**Independence - Freedom - Happiness**

No.: 2271/VPCNCL  
Regarding the conformity assessment  
results

*Hanoi, date 14 month 10 year 2016*

**To: LABORATORY OF RESPIRATORY VIRUS**  
**DEPARTMENT OF MICROBIOLOGY AND IMMUNOLOGY - PASTEUR**  
**INSTITUTE IN HO CHI MINH CITY**

Based on the surveillance visit report dated 12 - 13 July 2016,  
Based on the requests of the Certification Audit Team and the Review Committee dated  
22 September 2016.

**DIRECTOR OF BEREAU OF ACCREDITATION INFORMS THAT:**

Name of the organization recognized:

**LABORATORY OF RESPIRATORY VIRUS**

**Of**

**DEPARTMENT OF MICROBIOLOGY AND IMMUNOLOGY - PASTEUR**  
**INSTITUTE IN HO CHI MINH CITY**

Accreditation No. VILAS Med 012 according to the Decision No.: 520.2015 QD/VPCNCL  
dated 14 December 2015: Found to conform with the requirements for maintaining  
certification.

Sincerely.

***Recipients:***

- As mentioned above;
- Filling: Office;
- Laboratory Records.

## CERTIFICATO DI ACCREDITAMENTO Accreditation Certificate

Accreditamento n°  
Accreditation n°

**1411**

Rev. **1**

Si dichiara che  
We declare that

**VisMederi Srl**

Sede/Headquarters:  
[name]

è conforme ai requisiti  
della norma  
  
meets the requirements  
of the standard

UNI CEI EN ISO/IEC 17025:2005 "Requisiti generali per la competenza dei  
Laboratori di prova e taratura"

EN ISO/IEC 17025:2005 "General Requirements for the Competence of Testing  
and Calibration Laboratories" standard

quale **Laboratorio di Prova**  
as **Testing Laboratory**

[figure not shown]
L'accreditamento attesta la competenza tecnica del Laboratorio relativamente allo scopo riportato nelle schede allegate al presente certificato. Le schede possono variare nel tempo. I requisiti gestionali della ISO/IEC 17025:2005 (sezione 4) sono scritti in un linguaggio idoneo all'attività dei Laboratori di Prova, sono conformi ai principi della ISO 9001:2008 ed allineati con i suoi requisiti applicabili. Il presente certificato non è da ritenersi valido se non accompagnato dalle schede allegate e può essere sospeso o revocato in qualsiasi momento nel caso di inadempienza accertata da parte di ACCREDIA. La vigenza dell'accreditamento può essere verificata sul sito WEB ([www.accredia.it](http://www.accredia.it)) o richiesta direttamente ai singoli Dipartimenti.

*The accreditation certifies the technical competence of the laboratory limited to the scope detailed in the attached Enclosure. The scope may vary in the time. The management system requirements in ISO/IEC 17025:2005 (Section 4) are written in a language relevant to Testing Laboratories operations and meet the principles of ISO 9001:2008 and are aligned with its pertinent requirements. The present certificate is valid only if associated to the annexed schedule, and can be suspended or withdrawn at any time in the event of non fulfilment as ascertained by ACCREDIA. The in force status of the accreditation may be checked in the WEB site ([www.accredia.it](http://www.accredia.it)) or on direct request to appointed Department.*

[figure not shown]
Data di 1a emissione  
1st issue date  
**2013-12-18**

Data di modifica  
Modification date  
**2016-06-23**

Data di scadenza  
Expiring date  

## CERTIFICATO DI ACCREDITAMENTO

### Accreditation Certificate

Accreditamento n° **0002**  
Accreditation n°

Rev. **1**

Si dichiara che  
We declare that

**VisMederi Srl**

Sede/Headquarters:  
[name]

è conforme ai requisiti  
della norma  
meets the requirements  
of the standard

UNI EN ISO 15189:2013 "Laboratori medici - Requisiti riguardanti la qualità e la competenza"

ISO 15189:2012 "Medical Laboratories - Requirements for Quality and Competence" standard

quale **Laboratorio medico**  
as **Medical Laboratory**

L'accREDITAMENTO attesta la competenza tecnica del Laboratorio relativamente allo scopo riportato nelle schede allegate al presente certificato. Le schede possono variare nel tempo. I requisiti gestionali della ISO 15189:2012 (sezione 4) sono scritti in un linguaggio idoneo all'attività dei Laboratori medici, sono conformi ai principi della ISO 9001:2008 ed allineati con i suoi requisiti applicabili.

Il presente certificato non è da ritenersi valido se non accompagnato dalle schede allegate e può essere sospeso o revocato in qualsiasi momento nel caso di inadempienza accertata da parte di ACCREDIA.

La vigenza dell'accREDITAMENTO può essere verificata sul sito WEB ([www.accredia.it](http://www.accredia.it)) o richiesta direttamente ai singoli Dipartimenti .

*The accreditation certifies the technical competence of the laboratory limited to the scope detailed in the attached Enclosure. The scope may vary in the time. The management system requirements in ISO 15189:2012 (Section 4) are written in a language relevant to Medical Laboratories operations and meet the principles of ISO 9001:2008 and are aligned with its pertinent requirements.*

*The present certificate is valid only if associated to the annexed schedule, and can be suspended or withdrawn at any time in the event of non fulfilment as ascertained by ACCREDIA.*

*The in force status of the accreditation may be checked in the WEB site ([www.accredia.it](http://www.accredia.it)) or on direct request to appointed Department.*

Data di 1a emissione  
1st issue date  
**2015-05-22**

Data di modifica  
Modification date  
**2016-02-18**

Data di scadenza  
Expiring date  

### Criteria for Marked Vital Signs Abnormalities

Vital sign	Assessment criteria
Body temperature (oral)	
 
• Normal: 36.4 - 37.2 °C.
 
• Abnormal - NCS: 37.3 - 37.9°C; OR < 36.4°C and there are no clinical signs or symptoms which require intervention.
 
• Abnormal - CS: ≥ 38.0°C OR < 36.4°C and there are clinical signs or symptoms which need intervention
 

Blood pressure (mmHg)	
 
• Normal: 90 - 120 mmHg systolic OR 60 - 85 mmHg diastolic.
 
• Abnormal - NCS: 
 
Upward trend 
 
- 121 - 139 mmHg systolic AND/OR
 
- 86 - 89 mmHg diastolic
 
 
 
Downward trend 
 
- 85-89 mmHg systolic AND/OR 50 - 59 mmHg diastolic 
 
• For the participants who have grade 1 elevated blood pressure, the Investigator will judge if it is clinically significant or not based on the medical history and physical examination, e.g., history of elevated blood pressure, blood pressure monitoring and treatment, presence of clinical signs or symptoms which need intervention, presence of risk factors (obesity, too much alcohol, tobacco use); the Investigator should also refer to the local guideline for diagnosis and treatment of high blood pressure. If the findings are clinical significant, they should be graded according to the DAIDS Table For Grading the Severity in the protocol and MOP 04.
 
• Similarly, if the participants have < 85 mmHg systolic OR < 50mmHg diastolic; the Investigator will judge it is clinically significant when the participants have clinical signs or symptoms which need intervention.
 
 
 
 
 
 
 
• For the 2 cases above, the Investigator should record the reason for his assessment in the subject binders. 
 
• Grade 2 elevated blood pressure will be judged to be clinically significant.
 
 
 
• Note: 
 
• For those who have history of elevated blood pressure, they will be judged to be non-clinically significant and enrolled according to the criterium #4 if they are stable for the past 3 months and the medication dose is stable for at least 1 month preceding vaccination.
 
• For those who have clinically significant abnormalities, the study doctor will consult and refer the participants to the health facilities for diagnosis and treatment.
 
 
 

Vital sign	Assessment criteria
	

• Life-threatening blood pressure is defined to be grade 3 elevated blood pressure along with one of the following symptoms which require hospitalization indicated, e.g., headache, breathing difficulty, blurred vision, chest pain.

Pulse rate	

• Normal: 60 - 90 beats/min.

• Abnormal - NCS: 55 - < 60 beats/min or 91-100 beats/min.

• Abnormal - CS: < 55 beats/min, or > 100 beats/min and there are clinical signs or symptoms which need intervention or there are abnormal cardiac findings after examination. For this case, the Investigator should record the reason for his assessment in the subject binder.

• Note: There is no grading scale for pulse rate.

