### 9.1.3 Physical Examination

#### General Physical Examinations

Qualified study clinicians will conduct a physical examination of all participants at S1/D1. This physical examination will include the following:

- Recording of general appearance
- Physical examination of all organ systems. This includes the following:
  - neurologic examination, including cranial nerve examination
  - chest auscultation
  - examination of lymph nodes (axillary and cervical)
  - heart auscultation
  - abdomen palpation (to check for liver size)
- Measurement of the following vital signs:
  - body temperature
  - blood pressure
  - pulse/heart rate

\* Grade 1 elevated blood pressure (140 to < 160 mmHg systolic OR 90 to < 100 mmHg diastolic) will not be considered to be exclusionary at screening, unless judged to be clinically significant by the PI.

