**II. Definitions of terms used in the Table:**

Basic Self-care	Functions Adult Activities such as bathing, dressing, toileting, transfer/movement, continence, and feeding.
LLN	Lower limit of normal
Medical Intervention	Use of pharmacologic or biologic agent(s) for treatment of an AE
NA	Not Applicable
Operative Intervention	Surgical OR other invasive mechanical procedures.
ULN	Upper limit of normal
Usual Social & Functional Activities	Adult Adaptive tasks and desirable activities, such as going to work, shopping, cooking, use of transportation, pursuing a hobby, etc.

PARAMETER	GRADE 1 MILD	GRADE 2 MODERATE	GRADE 3 SEVERE	GRADE 4 POTENTIALLY LIFE-THREATENING
ESTIMATING SEVERITY GRADE				
Blood Pressure Abnormalities--Hypertension	140 to < 160 mmHg systolic OR 90 to < 100 mmHg diastolic	≥ 160 to < 180 mmHg systolic OR ≥ 100 to < 110 mmHg diastolic	≥ 180 mmHg systolic OR ≥ 110 mmHg diastolic	Life-threatening consequences in a participant not previously diagnosed with hypertension (e.g., malignant hypertension) OR Hospitalization indicated
SYSTEMIC				
Acute Allergic Reaction	Localized urticaria (wheals) with no medical intervention indicated	Localized urticaria with intervention indicated OR Mild angioedema with no intervention indicated	Generalized urticaria OR Angioedema with intervention indicated OR Symptoms of mild bronchospasm	Acute anaphylaxis OR Life-threatening bronchospasm OR Laryngeal edema
Chills	Symptoms causing no or minimal interference with usual social & functional activities	Symptoms causing greater than minimal interference with usual social & functional activities	Symptoms causing inability to perform usual social & functional activities	NA
Fatigue or Malaise Report only one	Symptoms causing no or minimal interference with usual social & functional activities	Symptoms causing greater than minimal interference with usual social & functional activities	Symptoms causing inability to perform usual social & functional activities	Incapacitating symptoms of fatigue or malaise causing inability to perform basic self-care functions

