## 17.5 VITAL SIGNS

Vital sign measurements include body temperature (oral), blood pressure (systolic and diastolic) and heart rate collected at Screening and Day 8 of the study.

The vital signs measurements, including abnormalities (grading for body temperature and blood pressure) and heart rate associated along with clinical significance (Yes/No) will be presented in the listings.

The following summaries will be provided for vital signs data:

- Actual and change from Baseline to Day 8
- Actual and change from Baseline to Day 8 by grade
- Shift from Baseline to Day 8 by grade
- Number and percentage of subjects by clinical significance
- Number and percentage of subjects shift from Baseline to Day 8 by clinical significance

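### The blood-pressure criteria sheet gives some readings two incompatible classes, and the SAP 17.5 tables by grade can miss readings that meet an Appendix A grade

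*Combined protocol and SAP*

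**What the plan says.** The sheet Criteria for Marked Vital Signs Abnormalities (section 16.1.10) sorts blood pressure as follows.

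- Normal is "90 - 120 mmHg systolic OR 60 - 85 mmHg diastolic".
- The upward-trend class of abnormal but not clinically significant (NCS) starts at "121 - 139 mmHg systolic AND/OR" and adds diastolic 86-89.
- Grade 1 goes to the investigator, who decides whether it is clinically significant (CS).
- For Grade 2 the sheet states: "Grade 2 elevated blood pressure will be judged to be clinically significant".
- Grade 3 appears only together with symptoms, as the definition of life-threatening blood pressure.
- For people with a history of elevated blood pressure, a note says "they will be judged to be non-clinically significant and enrolled according to the criterium #4 if they are stable for the past 3 months" and their medication dose has been stable for at least 1 month. It sets no upper grade.

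Protocol Appendix A grades hypertension when either component is raised. Grade 1 is "140 to < 160 mmHg systolic OR 90 to < 100 mmHg diastolic", Grade 2 is "≥ 160 to < 180 mmHg systolic OR ≥ 100 to < 110 mmHg diastolic", and Grade 3 is systolic 180 or more or diastolic 110 or more. Protocol 9.1.3 says that Grade 1 "will not be considered to be exclusionary at screening, unless judged to be clinically significant by the PI".

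On the eCRF, both the Screening Physical Exam form and the Targeted PE form open the blood-pressure grading scale only under Abnormal-CS. The footnote to Listing 16.2.8.2 restricts the grade in the same way. SAP 17.5 plans actual values and change by grade, "Shift from Baseline to Day 8 by grade", and tables by clinical significance. Shell Table 14.3.6.2, the shift by grade, names Listing 16.2.8.2 as its source.

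**The concern.** A classification that feeds a safety table should put each reading in one class. Here the Normal line uses OR while Appendix A also uses OR for the abnormal grades. A reading with one raised component can therefore satisfy both, and two clinicians could file it differently while each follows the sheet.

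The second conflict touches enrolment. For a stable known hypertensive with a Grade 2 reading, one line gives clinically significant; the other gives not clinically significant and enrolled.

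The third issue is the link between grade and clinical significance. A numeric grade and a clinical judgement are different quantities, but the data flow stores the first only when the second is positive. A table headed by grade would then show graded readings only where they were also judged clinically significant.

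**Working it through.** **1. Overlap, by example.** Inputs: the Normal and NCS ranges from the sheet, and the Grade 1 to 3 cut-offs from Appendix A.

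| Reading | Component in the Normal range | Other component | Also meets |
|---|---|---|---|
| 130/80 | diastolic 80 | systolic 130 | upward-trend NCS |
| 150/82 | diastolic 82 | systolic 150 | Grade 1 |
| 118/95 | systolic 118 | diastolic 95 | Grade 1 |
| 170/80 | diastolic 80 | systolic 170 | Grade 2 |
| 185/84 | diastolic 84 | systolic 185 | Grade 3 |
| 165/102 | none | both raised | Grade 2 only; not Normal |

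**2. Overlap, by enumeration.** Take all whole-number pairs with systolic 70-220, diastolic 40-130 and a difference of at least 10 mmHg (an assumed grid). The diastolic Normal range, 60-85, holds 26 values; the systolic Normal range is 90-120. Pairs that meet both Normal and a grade are:

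- Grade 1: systolic 140-159 (20 values) x 26 = 520. Systolic 90-120 with diastolic 90-99 adds 21 + 20 + ... + 12 = 165. Total 685, of 1,555 Grade 1 pairs.
- Grade 2: systolic 160-179 (20 values) x 26 = 520. Systolic 90-120 with diastolic 100-109 adds 11 + 10 + ... + 2 = 65. Total 585, of 1,855.
- Grade 3: systolic 180-220 (41 values) x 26 = 1,066. The pair 120/110 adds 1. Total 1,067, of 4,781.
- Normal and upward-trend NCS: 19 x 26 = 494, plus 25 + 24 + 23 + 22 = 94. Total 588.

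If both components had to be in range, the overlap with Grades 1 to 3 would be 0. That comparison only locates the cause in the connector; it does not say which clinical definition is right. The counts describe the logic of the rules and are not prevalences.

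**3. Lines that apply to an overlapping reading.** 150/82 meets Normal and the Grade 1 line. 170/80 meets Normal and the Grade 2 line. 185/84 without symptoms, in someone with no history, meets Normal and no other line, because the sheet mentions Grade 3 only with symptoms. Nothing on the sheet ranks these lines.

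**4. The known-hypertensive note.** Suppose 165/102 in a person whose condition has been stable for 3 months on a dose unchanged for 1 month. The Grade 2 line gives CS; the note gives NCS and enrolled. This conflict does not depend on the OR, since 165/102 never meets Normal. Protocol 9.1.3 does not settle it, because it covers Grade 1 only.

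**5. Route of the grade into the tables.** A reading called Normal or NCS has no grade field, so Listing 16.2.8.2 shows no grade and Table 14.3.6.2, built from that listing, has nothing to place. This covers three cases: a graded reading filed as Normal through the OR; a Grade 1 reading that the investigator properly calls NCS; and a Grade 2 reading called NCS under the note. The systolic and diastolic values themselves have fields on both forms whatever the finding.

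**The case against.** The best defence is that a sensible clinician would not file 170/80 as Normal when the same sheet says Grade 2 is clinically significant, and that Grade 1 has its own line with the reason to be written down. That stands, and it rules out a stronger inference: that Grade 1 to 3 hypertension in general passes screening as Normal and ungraded. Readings with both components outside the Normal ranges never meet Normal. Where the classes overlap, the documents show two competing lines, not a settled outcome.

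A reader might also infer that protocol 9.1.3 makes eligibility turn on the Normal call. It does not. It ties only Grade 1 to the investigator's judgement and does not mention the sheet. Entry otherwise rests on the health criterion in 5.2 and the investigator's opinion in 5.3, and 5.3 has no blood-pressure cut-off.

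It is also fair to say that recording a grade only for CS findings was deliberate: the sheet asks for grading when a finding is clinically significant. And no measurements are lost, since SAP 17.5 also summarises actual values and change. Both points stand, but neither makes a table headed by grade complete.

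Finally, the known-hypertensive conflict is conditional on stability, the bullet nesting in the available text is disordered, and the sheet refers to a manual (MOP 04) that is not among the documents and might set a precedence. That limits how firmly intent can be read. It does not remove the contradiction in the text as it stands.

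**Conclusion.** The point holds in three limited parts. First, Normal overlaps NCS and Grades 1 to 3 whenever one component is in range and the other is raised; this contradicts the sheet's own Grade 1 and Grade 2 lines, and Grade 3 without symptoms has no line of its own. Second, the Grade 2 line and the note on stable known hypertension give opposite answers on clinical significance, and the note goes on to enrolment. Third, the SAP 17.5 summaries by grade can omit readings that meet an Appendix A grade, if they take the grade from the eCRF as the source listing indicates. SAP 17.5 does not itself say where the grade comes from.

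The size is modest. Vital signs are not a named endpoint, and no primary analysis or sample-size figure changes. The calls are made under blinding, so the expected effect is under-reporting of graded readings in both arms; nothing here points to a bias between them. The documents give no blood-pressure distribution and no misfiling rate, so any count of affected participants would be guesswork.

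**What to change.** In SAP 17.5, derive the Appendix A grade at baseline and Day 8 from the recorded systolic and diastolic values, taking the higher grade of the two components, as Appendix A's OR wording implies. Derive Grades 1 to 3 this way and keep Grade 4 as recorded, since Appendix A defines it by consequences and not by a pressure. Keep the investigator's Normal, NCS or CS call as a separate variable for the tables by clinical significance. Give Table 14.3.6.2 a row and column for no grade: as it reads, the shell shows only grades 1 to 4, so a move from ungraded to graded has no cell.

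The sponsor should reconcile the Normal line with the Grade 1 to 3 lines, and the Grade 2 line with the known-hypertensive note, so that each reading meets one rule. Which clinical rule applies is for the sponsor to decide.

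The cost is a short derivation, one shell change and a reworded sheet, with no new data. The downside is more graded readings in the safety tables, some of them beside a call of not clinically significant; a footnote can explain the difference.

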### 10.4 Severity of Event

This study will use the Toxicity Table for Grading Adverse Events (see [appendix A](#)). For events not included in the table, the following guidelines will be used to quantify intensity not included on the table, the following guidelines will be used to quantify intensity:

Grade	Description for grading when an event is not on Toxicity Table
1 (Mild)	Mild symptoms causing no or minimal interference with usual social & functional activities with intervention not indicated.
2 (Moderate)	Moderate symptoms causing greater than minimal interference with usual social & functional activities with intervention indicated.
3 (Severe)	Severe symptoms causing inability to perform usual social & functional activities with intervention or hospitalization indicated.
4 (Life threatening)	Potentially life-threatening symptoms causing inability to perform basic self-care functions with intervention indicated to prevent permanent impairment, persistent disability, or death.

**Basic Self-care Functions – Adult:** Activities such as bathing, dressing, toileting, transfer/movement, continence, and feeding.

**Usual Social & Functional Activities – Adult:** Activities which adults perform on a routine basis and those which are part of regular activities of daily living, for example going to work, shopping, cooking, use of transportation or pursuing a hobby.

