### 11.1.1 Expedited Safety Review

Safety events listed in [table 1](#) require expedited PSRT review within 36 hours of submission of the safety information to data management and or SAE reporting system. Members of the PSRT will be notified of these events through the CRO pharmacovigilance system.

Event and relationship to study agent as assessed by investigator or CRO Pharmacovigilance Medical Monitor	Severity Grade
SAE, related	All grades
Unsolicited AE, related	4
Local reactions – erythema or induration	4

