2.* Body temperature (oral) [Body temperature]	[VSTEMCMP] [VSTEMP] Body temperature (oral)  °C [b] [VSTRE] Finding [A:1]  Normal [A:2]  Abnormal - NCS [A:3]  [VSTGR] Abnormal - CS Grading Scale [A:0]  Ungradable [A:1]  1 (38.0 - <38.6°C) [A:2]  2 (38.6 - <39.3°C) [A:3]  3 (39.3 - <40.0°C) [A:4]  4 (≥ 40.0°C)	
3.* Blood Pressure [Blood Pressure]	[VSBPCMP] [VSBPCOM] [SYSBP]  mmHg [b] [DIABP]  mmHg [b] Systolic Diastolic [VSBRE] Finding [A:1]  Normal [A:2]  Abnormal - NCS [A:3]  [VBSGR] Abnormal - CS Grading Scale [A:0]  Ungradable [A:1]  1 140 to < 160 mmHg systolic OR 90 to < 100 mmHg diastolic [A:2]  2 ≥ 160 to < 180 mmHg systolic OR ≥ 100 to < 110 mmHg diastolic [A:3]  3 ≥ 180 mmHg systolic OR ≥ 110 mmHg diastolic [A:4]  4 Life Threatening	
4.* Pulse Rate [Pulse Rate]	[VSHRCMP] [VSHR] Pulse Rate  beats/min [b] [VSHRE] Finding [A:1]  Normal [A:2]  Abnormal - NCS [A:3]  [HRSPEC] Abnormal - CS, Specify A200*	
Physical Examination [PE2SC]		
5.* Are there any abnormal and clinically significant PE findings? [Any abnormal and clinically significant PE findings?]	[PERES] [A:1]  Yes [A:2]  No If Yes, please complete Abnormal Findings below.	
6.*	PE number	Area/System
Abnormal Findings Entry [PE3SC]		
6.1 PE number [read-only] [PE number]	[PENUM] N3	
6.2.* Area/System [Area/System]	[PESYSPD] [A:1]  [PESYS] [cPESYS]  [A:2]  [PEDESOTH] Other, specify: A100*	
6.3.* Finding [Finding]	[PERES1] [A:1]  Abnormal, NCS [A:2]  [PECM] Abnormal, CS Please specify Current Medical Condition # A200*	
Key: [*] = Item is required [✓] = Source verification required [b] = Base Unit [*] = ASCII Only Note: Source verification critical settings made in InForm will override any settings made in Central Designer.		

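### The vital-signs criteria sheet defines life-threatening blood pressure more narrowly than Grade 4 in Appendix A, so one event can carry two grades

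*Combined protocol and SAP*

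**What the plan says.** **Protocol.** Section 10.4 sets the grading standard: "This study will use the Toxicity Table for Grading Adverse Events", meaning Appendix A. In the hypertension row of that appendix, Grade 2 is "≥ 160 to < 180 mmHg systolic OR ≥ 100 to < 110 mmHg diastolic", Grade 3 is "≥ 180 mmHg systolic OR ≥ 110 mmHg diastolic", and Grade 4 is "Life-threatening consequences in a participant not previously diagnosed with hypertension (e.g., malignant hypertension) OR Hospitalization indicated".

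**Criteria sheet.** Criteria for Marked Vital Signs Abnormalities, in section 16.1.10, has its own entry for life-threatening blood pressure, which "is defined to be grade 3 elevated blood pressure along with one of the following symptoms which require hospitalization indicated". Chest pain and blurred vision are among the examples that follow. In its bullet on Grade 1 readings, the sheet says of clinically significant findings that "they should be graded according to the DAIDS Table For Grading the Severity in the protocol", and it also names a study manual, MOP 04, which is not among the documents.

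**eCRF.** The Screening Physical Exam and Targeted PE forms print the mmHg ranges for Grades 1 to 3. The last option reads only "4 Life Threatening".

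**Where the grade is used.** SAP 17.5 plans vital-sign summaries by grade and a shift from baseline to Day 8 by grade, and Table 14.3.6.2 is the shell for the shift. Protocol 11.1.1 lists "Unsolicited AE, related" for expedited review by the Protocol Safety Review Team (PSRT) at Grade 4 only.

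**The concern.** Grades 1 to 3 rest on mmHg bands that are the same in Appendix A and on the eCRF. Grade 4 does not. It needs a verbal definition, the eCRF gives none, and the two documents that do give one differ. The sheet's entry uses the same term as the eCRF option, so an assessor could reasonably turn to it, while another assessor following section 10.4 would turn to Appendix A. The same finding could then be entered under two grades, at the most serious level of the scale.

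At stake is the consistency of the by-grade vital-sign tables and, if the grade is carried further, the severity recorded for an adverse event. The study has no data safety monitoring board and no formal pause rules (Protocol 11.1.2 and 11.2), so graded safety data reviewed by the PSRT are its main oversight.

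**Working it through.** No figure in the plan depends on this rule, so there is nothing to reproduce. The check is a comparison of the two rules.

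**Step 1: write each rule as conditions.**
- Appendix A, Grade 4 = (life-threatening consequences AND no previous diagnosis of hypertension) OR hospitalization indicated.
- Sheet, life-threatening = reading in the Grade 3 band (at least 180 systolic or 110 diastolic) AND a symptom for which hospitalization is indicated.

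The sheet does not print the numeral 4 beside its definition. The link to Grade 4 comes from the eCRF label and from the Appendix A column heading.

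**Step 2: compare them.** Anything that meets the sheet has hospitalization indicated, and that alone meets Appendix A. Every sheet case is therefore an Appendix A case, but not the reverse. The sheet's silence on previous diagnosis makes no difference: that limit belongs only to the first Appendix A alternative, and a sheet case always qualifies through the second.

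**Step 3: apply both to illustrative cases.** The readings are assumed. Where the sheet's definition is not met, the grade is the one given by the mmHg band.

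| Case | Appendix A | Sheet |
|---|---|---|
| 190/115, hospitalization indicated, no symptom | 4 | 3 |
| 175/105, hospitalization indicated, no symptom | 4 | 2 |
| 150/95, hospitalization indicated, no symptom | 4 | 1 |
| 185/112, life-threatening consequences, no previous diagnosis, no symptom requiring hospitalization | 4 | 3 |
| 185/112, chest pain requiring hospitalization | 4 | 4 |

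The sheet's symptoms are given as examples, so no symptom here means none that calls for admission, not merely none of those named. In the 175/105 and 150/95 cases symptoms do not matter, because the reading is below the Grade 3 floor.

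**Step 4: look for a tie-break.** Section 10.4 names Appendix A. The sheet points to the same table, but in its Grade 1 bullet; its life-threatening entry then states a separate rule. Appendix A's instruction to take the higher grade when a severity could fall under either of two addresses doubt within one scale. It does not rank two definitions.

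**Step 5: scale.** Protocol 13.3 plans 740 vaccinees. One participant moved between grades is 1/740 = 0.14% of that arm.

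**The case against.** The strongest reply is that the question of authority is already settled. Section 10.4 makes Appendix A the study's table, the sheet sends findings back to it, and nothing says that the sheet overrides it. The sheet classifies vital-sign readings, while unsolicited adverse-event severity is a separate eCRF field governed by 10.4. The manual that the sheet cites is not available, so nobody can tell from these documents what sites were told to enter. Much of this stands. It limits how far the inconsistency reaches. It does not remove it, because the sheet still states an operational rule that can give a different grade from the named table.

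Three stronger readings are tempting and should not be drawn.

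- **That the rules conflict in both directions.** Read literally, they do not: the sheet is a subset of Appendix A. A reverse conflict arises only if sites treat a named symptom, such as headache, as enough without hospitalization actually being indicated. The wording is awkward enough to allow that, but it is not the plain sense.
- **That the sheet decides what is entered.** The bare eCRF label does not show which definition was used, and the documents do not rank the two at Grade 4.
- **That a lower grade switches off expedited PSRT review.** Under Protocol 10.2 an event requiring inpatient hospitalization, or one that is life-threatening, is an SAE, and 11.1.1 expedites related SAEs at every grade. The Grade 4 row would matter only for a related event that met Appendix A Grade 4, was entered on the AE form with the sheet's lower grade, and was not also reported as an SAE.

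**Conclusion.** Wrong as written, and minor. The two definitions differ, and the difference has one direction: an event at Grade 4 under Appendix A can be graded 3, 2 or even 1 under the sheet, and never the other way round on a literal reading.

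The effect that the documents support is on the vital-signs form and on the Day 8 by-grade summaries and shift table. Any effect on unsolicited adverse-event severity assumes that sites copy the sheet's grade to the AE form, which no text tells them to do. Any effect on the expedited-review trigger assumes, in addition, that the event is not reported as an SAE.

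Few events, if any, are expected in adults enrolled as healthy or medically stable. The 0.14% figure shows the weight of a single event; it is not a forecast. No sample-size or immunogenicity figure is affected. The review takes no position on which clinical definition is right; the texts have to agree.

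**What to change.** Reconcile the life-threatening entry in the criteria sheet with the Grade 4 hypertension cell of Appendix A, so that one definition serves the vital-signs eCRF option, adverse-event severity under 10.4 and the trigger in 11.1.1. State that definition, or a reference to it, beside the eCRF option or in its completion guideline.

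Before database lock, run one blinded query for blood-pressure findings where hospitalization was indicated and the grade is below 4. The vital-signs forms have no field for that indication, so the query should draw on the hospitalization box of the SAE form, adverse-event entries for raised blood pressure, and the reasons that investigators record in the subject binders.

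The cost is one line of text and one data query. No new visits or measurements are needed.
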